## 5.0 Study Procedures

### 5.1 Study Design

#### Randomized Controlled Trial (RCT)

We will implement an RCT of EnCoRE with random assignment to: (1) Outpatient mental health treatment + EnCoRE, or (2) Outpatient mental health treatment + health and wellness (comparison) group. We will recruit half of the sample from the Baltimore VAMC and the other half of the sample split between the Perry Point VAMC and the Washington DC VA. We will recruit participants in rounds. Participants will complete assessments at baseline, post-treatment, and 3-month follow-up. The baseline appointment will include a diagnostic screening interview to determine final eligibility. If a veteran is determined to be ineligible after completing this interview then his or her study participation will be concluded. We will measure symptom and functional outcomes and evaluate potential moderators of outcomes including general cognitive ability, attitudes and beliefs, depression, and psychotic symptoms.

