#### Comparison Condition

The comparison condition will be a Health and Wellness self-management intervention providing education and support related to the management of physical and emotional well-being. This intervention will include 2 individual meetings at the start that will include educational content about health/wellness topics and instruction in relaxation training. A group component of the comparison condition will meet twice per week for 12 weeks (24 sessions). The curriculum for this group will be based on an existing program developed by another VISN 5 MIRECC investigator that is being used in other MIRECC/VA-funded trials. Similar in structure to EnCoRE, group sessions will be held twice per week for 60 minutes. Each Health and Wellness course will be led by a trained interventionist using a manualized curriculum. Sessions will focus on health and wellness issues and education on ways to better manage health-related concerns following a basic structure that includes: review of the previous session's material, new educational content, and discussion/application. Topics will include: 1) Overview, 2) Physical Activity (3 sessions), 3) Nutrition/Healthy Eating (3 sessions), 4) Managing Fatigue/Sleep (3 sessions), 5) Relaxation (3 sessions), 6) Tobacco cessation (3 sessions), 7) Substance Use (3 sessions), 8) Medication/Side Effects (3 sessions), 9) Review (1 session), and Closing (1 session). In addition, participants in this condition will be offered additional individual sessions if needed to practice relaxation skills and receive instruction in implementing them in real-world settings.

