EnCoRE will run for 14 weeks with 2 individual and 24 group sessions. Both the individual and group sessions will be audio-recorded for training and fidelity purposes. The individual sessions will be scheduled at the convenience of each participant and will both be completed before the group begins. Group sessions will be held twice per week for 12 weeks, plus linkage between EnCoRE and participants' treatment teams - will be delivered and coordinated by the study interventionist at each site to maintain continuity of the philosophy and message of the intervention, and ensure that participants have a single person to whom they can address questions or problems. The interventionist will be well-known to the site and will regularly talk with staff regarding study recruitment and operations. Group sessions will be small (4-6 people) format for 60 minutes. The group format allows participants to benefit from modeling and role-playing with peers. The small size provides ample opportunity for participants to get adequate practice, while minimizing demands for sustained attention. Group sessions follow a pre-determined order, but the intervention will be flexible such that topics can be reviewed as needed. While each session has a specific topic, activities are adjusted to meet the needs of each participant. For example, activities such as role-playing are tailored by asking participants to detail situations that they would encounter in which they could use these skills, and then are set up to be as realistic for each participant as possible. EnCoRE includes strategies aimed at teaching Veterans with schizophrenia and negative symptoms ways to (1) increase intrinsic motivation for goal-directed activities, (2) understand and overcome deficits in anticipatory pleasure, (3) reduce expectancies for failure, and (4) perform skillfully in new social situations.

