## 5.6 Data Analysis

Data will be screened for errors using frequency and contingency tables and univariate and bivariate plots before analysis. As the primary outcome measures are scales we expect (but will verify) that they are approximately normally distributed; if not, we will consider alternatives (e.g. transformation or a generalized linear model). Our primary analytical approach will be to compare EnCoRE versus control at post-treatment (Hypotheses 1 thru 4 below) after adjusting for BL scores. This is one type of analysis of covariance (ANCOVA) linear regression model that improves power by reducing residual variation. We will also check whether there is an interaction between baseline severity and treatment effect. If there is, we will report these results as well. We will conduct a similar analysis (adjusting for BL) to compare the conditions at FU while including the post-treatment assessment in a repeated measures model, as including these values can help reduce bias in the FU estimates when participants miss the FU but are assessed at PT. We will enter site as a fixed effect into the analysis models because there will only be 3 sites (in relatively close proximity). Because the groups will have rolling admission, we do not expect significant group effects, however we will verify this by calculating intra-group correlations (i.e. ICC's) and if model fit is improved, we will include group as a random effect in

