primary analysis models (then, the model would be a linear mixed model that includes adjustment for BL). In this case we will replace site with group in the model as sample size will not be sufficient to adjust for both. Viewed from another perspective, group is nested within site and is thus the more specific nested variable to be adjusted for. We will also check covariate balance (demographics, clinical characteristics) across the two conditions. Randomization should keep the two conditions in balance, however it is possible for imbalance to occur by chance. If a substantively relevant BL covariate significantly differs across the two conditions we will adjust for the covariate. Because this is a randomized trial, no covariates other than BL score of the outcome measure and site will be adjusted for a priori. To assess potential bias due to missing assessments, we will compare BL characteristics of participants who were versus were not assessed at PT/FU. We will check that attrition rates are comparable in the two conditions. Our procedures and analyses will be based on the intent-to-treat principle: we will attempt to assess all participants at PT and FU including those who discontinue treatment early. All available data will be included in the analyses. We expect to have assessments on 85% of the sample (i.e. 15% attrition) at PT and 80% (i.e. 20% attrition) at FU. To analytically address potential bias in the comparison of the conditions at PT due to missing assessments, we will conduct a sensitivity analysis by imputing missing outcome values using a regression multiple imputation approach that will produce unbiased estimates under the Missing at Random (MAR) assumption, similar to mixed effects models. If Non-Ignorable (NI) dropout is indicated we will further conduct a sensitivity analysis under departures from the MAR assumption using the procedure of Carpenter. SAS Procedures MI and MIAnalyze will be used. Similar procedures will be used for missing data at FU.

Specific Aim 1: Train therapists and refine the EnCoRE manual in a trial with approximately 6 Veterans with schizophrenia. Procedures are described in section 3C.

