#### Sample Size Considerations

We have powered this RCT for primary hypotheses 1 and 2 of Specific Aim 2 (two outcome measures). We consider the tests for the FU assessment as secondary. A medium effect size at PT (e.g. Cohen's  $d$  = .50) would generally represent a minimum clinically important difference. For example, for the primary outcome in H1, the CAINS Affective-Motivational Deficit Subscale (average rating range: 0–4), we know that  $d$ =.50 represents a .36 point difference in means between EnCoRE and control at PT which is slightly more than 1/3 of the distance

between anchor points (0=No impairment, 1=Mild deficit, 2=Moderate deficit, 3=Moderately Severe deficit, 4=Severe deficit). Because we are testing 2 hypotheses under Specific Aim 2, we specified the alpha level=.05/2=.025 for the sample size calculation. Power was set =.80. We expect 15% attrition at PT. For these specifications and under the primary analysis model, we would need a sample size of N=92 when the correlation between baseline and post-treatment outcome measure = .70. Although, setting this correlation to .70 is reasonable, this correlation could plausibly be lower, requiring the sample size to be greater. Therefore, we reset this correlation to be .63, and found that a sample size of N = 108 would then be required. Calculations were performed assuming a repeated measures design using the Sampsi command in Stata version 8.

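### The 80% power for N=108 assumes independent patients although both arms are treated in groups; the protocol makes the group effect conditional on model fit, and the SAP leaves its form and degrees of freedom unstated

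*Protocol*

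**What the plan says.** **Delivery.** Protocol section 5.1 describes EnCoRE as two individual sessions and 24 group sessions: "Group sessions will be small (4-6 people) format for 60 minutes". The comparison arm also has 24 group sessions: "Similar in structure to EnCoRE, group sessions will be held twice per week for 60 minutes". Its group size is not given.

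**Entry into groups.** Section 5.1 states "We will recruit participants in rounds" and says that the two individual EnCoRE sessions "will both be completed before the group begins". Section 5.6 gives a different picture: "Because the groups will have rolling admission, we do not expect significant group effects".

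**Protocol analysis.** Section 5.6 plans to calculate intra-group correlations. It then says "if model fit is improved, we will include group as a random effect in" the primary models. No fit criterion is named. If included, group replaces the fixed site effect, because "group is nested within site and is thus the more specific nested variable to be adjusted for".

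**Sample size.** Sample Size Considerations lists alpha .025 for each of two primary hypotheses, power .80, d = .50, 15% attrition at post-treatment and a baseline to post-treatment correlation r. This gives N=92 at r=.70 and N=108 at r=.63. The lower r is justified thus: "setting this correlation to .70 is reasonable, this correlation could plausibly be lower, requiring the sample size to be greater". Clustering is not mentioned.

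**SAP.** The Statistical Test of Hypothesis paragraph reports a mixed model with a random therapy-group effect, not conditional on fit. Baseline, post-treatment and follow-up are all responses, with equal arm means at baseline and an unstructured error correlation. The time points on which the group effect acts are not given, nor is a degrees-of-freedom method. The overview sets the threshold at .05 without adjustment for multiple comparisons.

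**The concern.** Members of a therapy group share peers and an interventionist, so their outcomes may be correlated. Even a modest correlation then raises the variance of the treatment contrast, and a power figure for independent patients is too favourable. The reason given for expecting no group effect sits poorly with the rest of section 5.1, and continuous admission would not in any case remove the shared peers and interventionist.

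Two analysis questions follow. Under the protocol's rule, real clustering can be left out of the standard errors whenever about 20 small groups fail to show it through model fit. Under the SAP, baseline is a response measured before randomization and therefore before any group meets. A single group intercept over all three time points forces the same group effect on baseline as on later visits, and so understates clustering that arises during treatment.

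**Working it through.** **1. The plan's own figure.** For ANCOVA, n per arm = 2(1−r²)(z.9875 + z.80)²/d².
- r=.70: 2(.51)(2.241+.842)²/.25 = 38.8; total 2×38.8/.85 = 91.2 (plan: 92).
- r=.63: 2(.6031)(2.241+.842)²/.25 = 45.9; total 2×45.9/.85 = 107.9 (plan: 108).

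Both reproduce with no clustering term, so the arithmetic is right for independent patients.

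**2. Power with clustering.** Assumptions, none of them in the documents: ICC .02, .05 or .10 as a share of the baseline-adjusted residual variance, and groups of five in both arms. With 15% attrition, 4.25 per group are assessed, so the design effect is 1+(4.25−1)×ICC = 1+3.25×ICC, or 1.065, 1.163 and 1.325. About 108/5 = 22 groups leave 20 df.

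The variance is V = 2(.6031)(1+3.25×ICC), with 45.9 assessed per arm and λ = .5/√(V/45.9). Normal-reference power is Φ(λ−z). The t version is the probability that a noncentral t on 20 df with noncentrality λ exceeds its critical value (2.423 at alpha .025, 2.086 at .05). Example at ICC .05: V = 1.206×1.1625 = 1.402, λ = .5/.1748 = 2.861, and Φ(2.861−2.241) = .73.

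| r=.63 | ICC 0 | .02 | .05 | .10 |
|---|---|---|---|---|
| alpha .025, z | .80 | .77 | .73 | .67 |
| alpha .025, t 20 df | .74 | .71 | .67 | .61 |
| alpha .05, z | .87 | .85 | .82 | .76 |
| alpha .05, t 20 df | .83 | .81 | .78 | .72 |

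**3. Timing of clustering.** Now take the ICC as a share of total variance (alpha .025, r=.63, z). If all clustering arises after baseline, power is .76/.69/.60 at ICC .02/.05/.10. If it is constant from baseline, adjustment for baseline removes most of it. With m=5, ICC .05: the group-mean variance is .05+.95/5 = .24, the covariance is .05+.58/5 = .166, and V = 10(.24−.166²/.24) = 1.252 against 1.206 unclustered (+3.8%). Power is then .79/.78/.77.

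**4. Protocol rule.** If real clustering is left out of the model, true two-sided error at nominal .05 is about 2[1−Φ(1.96/√DE)]: 5.8%, 6.9% and 8.9% at residual-share ICC .02, .05 and .10. A fit-dependent rule mixes trials with and without the term, in proportions that depend on the unnamed criterion.

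**5. SAP, only if the group effect is one intercept spanning baseline.** A large-sample fit of the three-time model was made (equal baseline means, unstructured residual, all correlations .63, five per group, complete data), and its model-based standard error was compared with the true one. At total-variance ICC .05 and .10 the ratio is 1.00 and 1.00 if clustering is constant, .97 and .95 if the baseline group variance is half the later one, and .87 and .78 if clustering is entirely post-baseline. With type I error = 2[1−Φ(1.96×ratio)]:
- constant from baseline: 5.0% and 5.0%;
- half at baseline: 5.7% and 6.4%;
- entirely post-baseline: 8.7% and 12.4% (6.5% at ICC .02).

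Total-variance ICCs of .05 and .10 correspond to residual shares of .05/.6031 = .083 and .10/.6031 = .166, so these figures are not on the same scale as the table.

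**The case against.** The strongest reply is that clustering is handled. The protocol plans to estimate ICCs, and the later SAP fits the group effect whatever the fit. That stands. A reader might infer that the reported analysis ignores clustering; the SAP says otherwise, and the inflation in step 4 belongs to the protocol's rule alone.

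A reader might also infer that the SAP's standard errors are wrong and its type I error is near 12%. The documents do not support this. That figure needs a single intercept, clustering wholly after baseline and a total-variance ICC of .10 together. Baseline clustering is possible because groups are nested in site, and with constant clustering the error rate is exactly nominal. The SAP point is therefore missing detail.

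Third, choosing r=.63 when .70 was thought reasonable leaves a margin. With a normal reference it does: at r=.70 and alpha .025, power is .84/.81/.75 at ICC .02/.05/.10. With 20 df, however, it is already .79 at ICC .02, so the margin does not cover an analysis whose degrees of freedom are based on groups.

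Finally, rounds and rolling admission can be read together: waves of recruitment may feed groups that admit members over time, and the individual sessions may precede each participant's own entry. A reader might call this a contradiction; it is an unclear description.

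**Conclusion.** The point holds for the power statement. N=108 contains no allowance for therapy-group clustering, and at alpha .025 and r=.63 the stated 80% applies only to independent patients with a normal reference. This is certain from the reproduction. The size of the shortfall is not: it rests on an assumed ICC, its scale and timing, and groups of five in both arms. At the protocol's alpha it runs from 3 to 13 points with a normal reference. With 20 df power is .74 before any clustering and .61 at ICC .10. At the SAP's alpha of .05, power stays above .80 at ICC .02 under either reference. At ICC .05 it is .82 (z) or .78 (20 df).

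On the analysis, the protocol's fit condition is a weakness that the SAP has already removed. The SAP's remaining gap is the unstated form and degrees of freedom of its group effect. Whether this affects the primary tests cannot be settled from the text. The point should be fixed, but it does not show that the reported results are invalid.

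**What to change.** 1. Restate the power of N=108 over a stated ICC range, using the same reference distribution as the analysis. Name the ICC scale, the group size in each arm and the alpha.
2. Remove the fit condition from protocol section 5.6, so that it matches the SAP's unconditional group effect.
3. State in the SAP, which is written in the past tense, the form of the group effect and the degrees of freedom that were used. If it was a single intercept, report as a sensitivity analysis a model whose group effect acts at post-treatment and follow-up without being forced to equal baseline, with small-sample degrees of freedom.
4. Clarify how patients enter groups, so that rolling admission in section 5.6 can be read together with the rounds and the order of sessions in section 5.1.

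Cost: wording, one additional model specification, a less favourable power figure, and 95% confidence intervals about 6% wider (2.086/1.960 = 1.064 for t on 20 df against z). No extra patients are needed.

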### Hypotheses

Hypothesis 1 (H1): Veterans exposed to EnCoRE will have lower mean scores than those in the control condition on the affective-motivational deficit subscale of the CAINS at post-treatment. The EnCoRE group will continue to have a lower mean than the control group at FU (secondary hypothesis). . Letting Y1, Y2, and Y3 be values for the motivational deficit subscale of the CAINS at BL, PT, and FU respectively, and Tx condition the treatment indicator (Tx condition=1, if EnCoRE; Tx=0 if control condition), the analysis model for Hypothesis 1 (post-treatment) will be:  $Y_2 = Y_1 + \text{Site (or Group)} + \text{Tx condition} + \text{error}$  (ANCOVA). Substantively relevant BL covariates found to significantly differ between treatment conditions, even after randomization, would be added. We will also check if there is a covariate by treatment interaction in this case. Significance test of the Tx condition coefficient will test hypothesis 1. The analysis model for the

comparison at FU will be similar, but will include Y2 and Y3 as repeated responses and include a random effect to account for correlation between the two. Thus, it will be a linear mixed model with adjustment for BL (Y2 and Y3 repeated response and adjustment for Y1). A time and group-by-time interaction term will be added (time indicating FU versus PT) in order to estimate the difference of means at FU assessment. A specified contrast using the mixed model will test the hypothesis that the mean affective-motivational deficit in the EnCoRE condition will continue to be less than in the control condition.

Hypothesis 2 (H2): Veterans exposed to EnCoRE will have a higher mean score than controls at post-treatment on the SFS and RFS. The EnCoRE group will continue to have higher a mean score than control at the 3 month FU. The analysis model for H2 will be parallel to those for H1.

Hypothesis 3 (H3): Veterans exposed to EnCoRE will have higher mean scores than controls at post-treatment and at FU on the UPSA-B total score.

Hypothesis 4 (H4). Veterans exposed to EnCoRE will have higher mean ratings on the MARS than control at PT and FU. Analysis models for H4 will be parallel to those for H1.

Hypothesis 5 (H5): General cognitive ability and symptoms of psychosis will not impact the effectiveness of the intervention for negative symptoms and community functioning at PT and FU (See analysis below for H6).

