Secondary Aim 1: Test the efficacy of EnCoRE in producing positive changes at PT and FU on a second measure of social/community functioning (UPSA-B). Hypothesis 3 (H3): Veterans exposed to EnCoRE will have higher mean scores than controls at post-treatment and at FU on the UPSA-B total score.

Secondary Aim 2: Test the efficacy of EnCoRE in producing positive changes at PT and FU on mental health recovery. Hypothesis 4 (H4). Veterans exposed to EnCoRE will have higher mean ratings on the MARS than control at PT and FU. Analysis models for H4 will be parallel to those for H1.

Secondary Aim 3: Assess the modifying effect of covariates on the effectiveness of EnCoRE including general cognitive ability and psychotic symptoms. Hypothesis 5 (H5): General cognitive ability and symptoms of psychosis will not impact the effectiveness of the intervention

for negative symptoms and community functioning at PT and FU (See analysis below for H6). Hypothesis 6 (H6): Greater ratings of consumer participation in and satisfaction with the intervention will be associated with better PT and FU outcomes. For each of the potential modifiers in H5 and H6, we will re-fit the primary analysis model for PT outcomes after adding two terms, the potential modifier and the interaction term between the treatment condition indicator (Tx condition) and the potential modifier. The variable will be a modifier if the coefficient for the interaction term is statistically significant ( $p$ -value<.05). A similar model will be used to assess modification at FU but there will be additional interaction terms with time (including 3-way interaction time\*treatment condition\*modifier), in order to estimate modifying effects at FU (i.e. separate effects at FU vs. PT).

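### H5 predicts no modification by cognition or psychosis symptoms, but its only decision rule is interaction p<.05, so the plan cannot tell no impact from an inconclusive result

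*Protocol*

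**What the plan says.** H5 appears in the Protocol under Hypotheses and again in section 5.6 under Secondary Aim 3. It is worded as a prediction of absence: "General cognitive ability and symptoms of psychosis will not impact the effectiveness of the intervention". The outcomes and time points it covers are given in the same sentence: "symptoms of psychosis will not impact the effectiveness of the intervention for negative symptoms and community functioning at PT and FU". For the method, H5 points to H6. There the primary model is re-fitted after "adding two terms, the potential modifier and the interaction term between the treatment condition indicator (Tx condition) and the potential modifier", with further time interactions for follow-up. The criterion is "The variable will be a modifier if the coefficient for the interaction term is statistically significant", at p<.05.

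Neither document states a smallest relevant interaction, an equivalence margin, a confidence-interval criterion or the power of any interaction test. Sample Size Considerations says "We have powered this RCT for primary hypotheses 1 and 2 of Specific Aim 2 (two outcome measures" and treats the follow-up tests as secondary.

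The SAP (Statistical Test of Hypothesis) describes moderator analyses for the DAS, the SARA-Q and, for the SFS outcome, baseline CAINS MAP, each split at the median. It does not mention cognition or psychosis symptoms as moderators.

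**The concern.** The p<.05 rule suits a hypothesis that predicts an effect, as H6 does. H5 predicts the opposite. Applied to H5, the rule yields either a significant interaction, which contradicts H5, or a non-significant one, which is the only result consistent with it. The plan has no third category for data too imprecise to decide, so low power works in favour of the hypothesis.

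At stake is a statement that EnCoRE works regardless of cognitive ability or psychosis symptoms, made from data that could not have shown otherwise. The Protocol looks ahead to a larger implementation trial, and such a statement could inform how it is designed.

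**Working it through.** **Inputs** (Protocol, Sample Size Considerations unless noted)
- Planned main effect d = .50, which "represents a .36 point difference in means between EnCoRE and control at PT". The implied outcome SD is .36/.50 = .72 points.
- "we specified the alpha level=.05/2=.025 for the sample size calculation"; "Power was set =.80".
- Baseline to post-treatment correlation r = .63 (first .70).
- Attrition 15% at post-treatment, so 108 × .85 ≈ 92 assessed. Attrition 20% at follow-up (section 5.6), so 108 × .80 ≈ 86.
- Equal allocation (Randomization Procedures).

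**Reproducing the stated sample size.** Sidedness is not stated; two-sided .025 reproduces the figures. Per arm, n = 2(1 − r²)(2.241 + .842)²/.50², where (2.241 + .842)² = 9.505.
- r = .70: 2 × .51 × 9.505/.25 = 38.8, so 39 per arm; 78/.85 = 91.8, or 92 as stated.
- r = .63: 2 × .6031 × 9.505/.25 = 45.86 per arm; 91.72/.85 = 107.9, or 108 as stated (109 if each arm is first rounded up to 46).

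**Precision of the interaction at post-treatment.** The residual SD is √(1 − .63²) = .777 outcome SDs.
- Main effect: SE = 2 × .777/√92 = .162.
- Continuous modifier, per SD of the modifier: SE = .162; 95% CI half-width 1.96 × .162 = .32.
- Median-split modifier, difference in effect between halves: SE = 2 × .162 = .324; half-width .63.

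**Power at two-sided .05.** The documents give no interaction size, so a range is shown. For a continuous modifier, power = Φ(slope/.162 − 1.96), plus a negligible opposite tail:

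| Slope (SD per SD) | Power |
|---|---|
| .10 | 10% |
| .20 | 24% |
| .25 | 34% |
| .30 | 46% |
| .50 | 87% |

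80% power needs (1.96 + .842) × .162 = .45 SD per SD.

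**An interaction as large as the planned effect, .50 SD between the lower and upper halves of the modifier.**
- Modifier kept continuous, as the Protocol model allows, and assumed roughly normal: the two half-means are 1.60 SD apart, so the slope is .50/1.60 = .313. Power = Φ(.313/.162 − 1.96) = 49%. 80% power needs .45 × 1.60 ≈ .72 SD between halves.
- Modifier split at the median, as the SAP does for other variables: power = Φ(.50/.324 − 1.96) = 34%. 80% power needs .91 SD.

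Simulating the ANCOVA with site gives slightly lower values: 31% for a slope of .25, 46% for .313, and 83% for .50.

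**Follow-up.** With 86 assessed, and assuming that the same correlation holds, the SE is 2 × .777/√86 = .167 and power for a slope of .25 is 32%.

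**What a margin would require.** The 95% CI half-width of .32 exceeds .25, so a margin of .25 SD per SD could not be met even if the estimate were exactly zero. Two one-sided 5% tests at that margin, with a true interaction of zero and 80% power, need about 331 assessed (389 randomised). A margin of .50 SD per SD would need about 83 assessed (98 randomised), but it tolerates .50 × 1.60 = .80 SD between halves, more than the whole planned effect.

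**The case against.** The strongest reply is that the plan nowhere says a non-significant interaction confirms H5. The criterion defines only when a variable is a modifier, and Secondary Aim 3 is worded neutrally, as an assessment of modifying effects. This is correct as to the text. A reader might infer that the Protocol commits itself to accepting the null; it does not do so in words. What remains is that H5 predicts absence and the plan provides no other criterion for judging it.

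Second, the power problem should not be overstated. A reader might infer that non-significance is likely even when moderation is large. The figures do not support that: power is 87% for .50 SD per SD, and also 87% for 1.0 SD between halves under a median split. Nor should the 34% split-half figure stand alone, because the Protocol does not dichotomise the H5 modifiers; with a continuous, roughly normal modifier the corresponding figure is 49%. Both remain well below 80%.

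Third, a reader might infer that the H5 result would decide who is offered EnCoRE later. No section uses H5 for eligibility, and the Protocol draws its adjustments before an implementation trial from the qualitative interviews.

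Fourth, the SAP, dated April 2021, omits cognition and psychosis symptoms as moderators, so an H5 claim may never be made. That is possible, but silence does not establish that H5 was dropped, and the Protocol text is the only plan for it.

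**Conclusion.** The concern holds in limited form. H5 is a hypothesis of no modification judged by a rule that cannot separate no impact from too little information. At the planned size, moderation about as large as the planned effect would be missed about half the time with a continuous modifier and about two times in three with a median split. Only steep interactions, about .45 SD per SD or more, would be found with 80% power.

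These figures assume 92 assessed, r = .63, equal arms, a modifier unrelated to baseline score and, for conversion to halves, a roughly normal modifier. The interaction sizes are illustrative, since the documents give none. The consequence is confined to a secondary aim; the H1 and H2 tests are untouched.

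**What to change.** For H5, state that p≥.05 is not evidence of no modification, and label the analysis exploratory. Keep each modifier continuous. Report the interaction estimate with its 95% CI, and the treatment effect at stated low and high modifier values, at both time points. Describe a non-significant result as inconclusive unless the CI lies wholly inside a margin that the sponsor justifies in advance, with its units given (per SD of modifier, or between halves). A margin of .25 SD per SD should not be adopted in the expectation of meeting it at this sample size.

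The SAP should say whether H5 is still planned and, if so, carry the same rule.

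The change needs no new data, no larger sample and no alteration to the primary tests. Its cost is that the likely H5 conclusion weakens from no impact to inconclusive.
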